9.3.1. Definitions

Kansas City Cardiomyopathy Questionnaire (KCCQ) Score: It is a Patient-reported outcome composed by 23-item, KCCQ that takes 4-6 min to complete. A self-administered questionnaire will be used to measure the patient's perception of their health status within a 2-week recall period. The domains of this scale are: Symptom, Physical function, Social Limitation, self-efficacy, Symptom stability, and Quality of Life. The clinical summary is calculated including the domain Physical limitation and Symptoms. The overall summary score combines total symptoms, physical and social limitation, and Quality of life. The score for each domain has a range from 0-100 where 0 is considered worst health and 100 the best health. Changes in the Overall summary of 5, 10 and 20 points have been considered small but clinically important, moderate to large, and large to very large changes, respectively (12). The scale has been translated and validated to Spanish of Colombia (15).

Perugini grading scale: It is a semi-quantitative method of scoring cardiac uptake following injection of 99mTc-DPD, 99mTc-Pyrophosphate or 99mTc-HMDP scintigraphy (16). It is classified as:

- grade 0: no cardiac uptake and normal rib uptake
- grade 1: cardiac uptake which is less than rib uptake
- grade 2: cardiac uptake with intensity similar rib uptake
- grade 3: cardiac uptake greater than rib uptake with mild or absent rib uptake

6 Minute walk test: It is considered as an alternative to cardiopulmonary exercise test for risk stratification in patients with Heart Failure. It is a simple test that requires no specialized equipment or physicians. It assesses the functional capacity while the patient walks on a flat, solid surface in a period of 6 min (13).

Hospitalization: It is defined as a nonelective admission to an acute care setting for medical therapy that results in at least a 24-hour stay (17).

Cardiovascular causes of hospitalization: The following diseases were considered as cardiovascular causes of hospitalization only it was considered the primary diagnosis (17):

- Heart failure
- Arrhythmia: When the patient is hospitalized by bradyarrhythmia, atrial, or ventricular rhythm disorders of the heart.
- Transient ischemic attack
- Stroke

PFIZER CONFIDENTIAL

CT24-WI-GL02-RF01 6.0 Non-Interventional Study Protocol Template For Primary Data Collection Study 01-

Aug-2023

Page 29 of 57

**CLINICAL AND MEDICAL CONTROLLED DOCUMENT (CMCD)
REQUIRED FORM/TEMPLATE**

Identifier	Version	Title	Effective Date
CT24-WI-GL02-RF01	6.0	NON-INTERVENTIONAL STUDY PROTOCOL TEMPLATE FOR PRIMARY DATA COLLECTION STUDY	01-Aug-2023

- Myocardial infarction
- Unstable angina
- Pulmonary embolism or peripheral arterial/vascular disease
- Peripheral emboli
- Venous thrombosis
- Other vascular reasons or complications.

Persistence: It will be calculated counting the days number covered to discontinuation from the index date to the end of the follow-up period. Discontinuation is considered as the end of the day of supply of the previous prescription.

Adherence: It will be measured by report through the Popit Sense device (18). This device identifies remotely in real-time when medications are taken. The information is gathered in Popit Cloud. The information needs to be downloaded through the Popit App into the smartphone. This outcome is measured only to patients that have access to the Popit Sense device. The Popit Sense devices are provided by the Pfizer Patient program to patients that are part of this program.

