- Comorbidities (Heart failure at early age, any cardiac arrhythmias or conduction disorders, type of any cardiac arrhythmias or conduction disorder, diabetes mellitus, hypertension, sleep apnea, chronic kidney diseases, intracardiac thrombosis, stroke, polyneuropathy, orthostatic hypotension, erectile dysfunction, glaucoma)
- Adherence
- Persistence
- Hospitalization
- Quality of Life (KCCQ-OS)
- Cardiovascular functionality (6-MWT and scintigraphy)
- Hospitalization
- **Data sources**

There will be several sources of information. From the medical record provided by the patient will be abstracted the demographic and clinical characteristics related to diagnosis, comorbidities, and treatment at baseline, as well as the previous medications to manage CA. Other sources will be the patient to confirm or complete the information associated with it.

The study will be performed in approximately 6 Colombian Health Provider Institution (IPS, in its Spanish acronym) whose population includes patients with ATTR-CM diagnosis in the period established. These sites will be in four Colombian cities (Bogotá, Medellin, Cali, and Barranquilla) which have a cardiologist with experience in diagnostic and management of ATTR-CM.

During the follow-up, the patient will provide the information about changes in the treatment, issues to supply tafamidis, and hospitalization which can be confirmed with the summary of the medical records of the patient. The quality of life will be measured using the KCCQ scale through call or face to face meeting. 6-MWT and scintigraphy will be abstracted from medical records.

- **Study size**

Sample size is not required for being observational and descriptive study. The expected number of patients eligible for the study is close to fifty considering the number of patients identified with the diagnosis and the access to the treatment.

PFIZER CONFIDENTIAL

CT24-WI-GL02-RF01 6.0 Non-Interventional Study Protocol Template For Primary Data Collection Study 01-

Aug-2023

Page 14 of 57

**CLINICAL AND MEDICAL CONTROLLED DOCUMENT (CMCD)
REQUIRED FORM/TEMPLATE**

Identifier	Version	Title	Effective Date
CT24-WI-GL02-RF01	6.0	NON-INTERVENTIONAL STUDY PROTOCOL TEMPLATE FOR PRIMARY DATA COLLECTION STUDY	01-Aug-2023

• **Data analysis**

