9. RESEARCH METHODS

9.1. Study design

The study will be a non-interventional, descriptive, and longitudinal prospective study with primary data collection that involves sites/investigators. The patients must be diagnosed before enrollment with ATTR-CM and prescribed with tafamidis following indications approved by National Institute for Drug and Food Vigilance (INVIMA) in Colombia. The patients will be followed up from the index date until patient i) have deceased, ii) have decided to withdraw from the study, iii) have terminated of treatment, iv) have been lost to follow up, or, v) finalize the 24 months of following up, the event that happens first. The index date will be defined as the date for the first prescription of tafamidis.

The patients that were prescribed with tafamidis before August of 2023 will be recruited. In the cases where the patients were prescribed before starting the study, all previous information will be collected from the data provided by the patients. The quality of life will be evaluated when the patient accepts to participate and signs the informed consent.

Quality of life, adherence, concomitant treatment, hospitalization for any causes, cardiovascular functionality will be measured 24 months after the prescription of tafamidis. Twelve months before the index date, treatments, and frequency of hospitalization for any causes will be measured (Table 1).

There will be two sources of information. Clinical and demographic information and death at the baseline will be abstracted from the medical record while the data related to hospitalizations, cardiovascular functionality, quality of life will be collected directly from the patients using validated questionnaires and structured interviews. Thus, in this case the report form (CRF) will serve as a source document.

In patients who have been prescribed with tafamidis more than 1 month and have not received the drug by the HMO yet, the first time of administration of tafamidis will be considered in the analysis. It will be considered as limitation of access. Any delay of supply for treatment will be considered limitation of access which will be assessed during the follow-up.

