The scale of quality of life named Kansas City Cardiomyopathy Questionnaire (KCCQ) (12) will be used after the acceptance to participate in the study by the patients with the signing of informed consent. In the statistical analysis will be considered the date to start tafamidis, the date of prescription of tafamidis and the time to start the measurement of QoL.

Data collection will be conducted with a CRF. This will be validated by two research centers to ensure feasibility of data collection, availability of the data as well as source documents and accurate definition of the study variables. The research staff at the participating centers will be trained in data extraction and completion of CRF.

The patients will be reached out to every three months±15 days through a phone call by a healthcare professional of the site. During this interview, the professional will perform a

PFIZER CONFIDENTIAL

CT24-WI-GL02-RF01 6.0 Non-Interventional Study Protocol Template For Primary Data Collection Study 01-

Aug-2023

Page 21 of 57

**CLINICAL AND MEDICAL CONTROLLED DOCUMENT (CMCD)
REQUIRED FORM/TEMPLATE**

Identifier	Version	Title	Effective Date
CT24-WI-GL02-RF01	6.0	NON-INTERVENTIONAL STUDY PROTOCOL TEMPLATE FOR PRIMARY DATA COLLECTION STUDY	01-Aug-2023

standardized interview with structured questionnaires to guarantee that the data collection process will be harmonized among patients. The interview could be in the site, if the patient received clinical care in there or she decided to move to it. Both collection data are completely accepted in the study.

The 6 min walk test (6MWT) and scintigraphy will be conducted based on the decision of cardiologist or responsible physician based on the guideline of the institution or medical practice. This study does not suggest these tests or is limited to them. They will be abstracted from medical records of patients who had measured them (13).

All assessments described in this protocol will be performed as part of normal clinical practice or standard practice guidelines for the patient population and healthcare provider specialty in Colombia where this noninterventional study is being conducted.

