9.4. Data sources

There will be several sources of information. From the medical record provided by the patient will be abstracted the demographic and clinical characteristics related to diagnosis, comorbidities, and treatment at baseline, as well as the previous medications to manage CA. Other sources will be the patient to confirm or complete the information associated with it.

During the follow-up, the patient will provide the information about changes in the treatment, issues to supply tafamidis, and hospitalization which be confirmed with the summary of the medical records of the patient. The quality of life will be measured using the KCCQ scale through call or face to face meetings. 6-MWT and scintigraphy will be abstracted from medical records.

Adherence will be measured using the information available in the Popit sense device. It is only available in patients that use this device. If the patient does not have access to Popit, it will not be a limitation to participate in the study, only that this variable will be not measured for them. These scales have been validated (12) and translated to Spanish of Colombia (14).

PFIZER CONFIDENTIAL

CT24-WI-GL02-RF01 6.0 Non-Interventional Study Protocol Template For Primary Data Collection Study 01-

Aug-2023

Page 30 of 57

CLINICAL AND MEDICAL CONTROLLED DOCUMENT (CMCD) REQUIRED FORM/TEMPLATE

Identifier	Version	Title	Effective Date
CT24-WI-GL02-RF01	6.0	NON-INTERVENTIONAL STUDY PROTOCOL TEMPLATE FOR PRIMARY DATA COLLECTION STUDY	01-Aug-2023

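### The KCCQ is defined as self-administered but collected by staff interview, by phone or on site, and mode is not recorded, so a shift in mode could pass unseen as a change in quality of life

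*Protocol*

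**What the plan says.** The protocol describes the administration of its primary instrument in two ways.

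- **Definition (9.3.1).** "A self-administered questionnaire will be used to measure the patient's perception of their health status within a 2-week recall period".
- **Data sources (9.4; the abstract is near-identical).** "The quality of life will be measured using the KCCQ scale through call or face to face meetings".
- **Contacts (9.1).** "The patients will be reached out to every three months±15 days through a phone call by a healthcare professional of the site". That professional carries out a "standardized interview with structured questionnaires to guarantee that the data collection process will be harmonized among patients".
- **Place (9.1).** "The interview could be in the site, if the patient received clinical care in there or she decided to move to it", followed by "Both collection data are completely accepted in the study".
- **Referred patients (9.2).** Those who stay with another institution may have their data collected by virtual interview.
- **First KCCQ (9.1).** "The quality of life will be evaluated when the patient accepts to participate and signs the informed consent". The mode is not stated.
- **Table 2.** The KCCQ-OS score is listed per visit with interview as its source. Mode of administration is not a listed variable.

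Mode is also absent from the subgroups (9.7.3.2), the model terms (9.7.5.2) and the limitations (9.9). Section 9.7.1 frames the quality-of-life result as change from baseline over 24 months.

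**The concern.** A site that follows 9.3.1 would hand the patient a form. A site that follows 9.1 and 9.4 would ask the questions. With about six sites, both practices could occur. Even if every site interviews, a patient may be interviewed by phone at one visit and in person at the next, because nothing fixes one mode per patient.

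Patients may answer a health-status questionnaire differently on paper, by phone and face to face. A comparative study could hope for the same mix of modes in each arm, so that the effect largely cancels. This study has one cohort and reads change within patients, so nothing cancels a shift in mode between the first and later KCCQs.

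The gap lies in data collection. If mode is never recorded, no later analysis plan can examine it.

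**Working it through.** The protocol gives no figure on this point to reproduce. The check has two parts.

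**1. The texts side by side**

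| Question | 9.3.1 | 9.1, 9.4, Table 2 |
|---|---|---|
| Who completes the KCCQ? | The patient | A site professional, by interview |
| Setting | Not stated | Phone or on site (9.2 adds virtual) |
| Same mode throughout for a patient? | Not stated | Not required; both accepted |
| Mode recorded? | Not stated | Not in Table 2 |

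Self-completion cannot occur in a phone interview as described. It is not ruled out at a site meeting, so the text leaves room for three modes.

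**2. What a mode shift does to the change score**

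Let m be the mean difference in score, in points, between a second mode and the first. Then:

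observed mean change = true mean change + m × (share moving to the second mode − share moving back)

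Three consequences follow.

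- A patient who keeps one mode contributes no mode bias to their change, whichever mode it is.
- Balanced switching cancels in the mean: 25% each way gives m × (0.25 − 0.25) = 0. Individual changes are still distorted, so spread increases.
- Only the net one-way share biases the mean.

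The protocol gives neither m nor the net share. With **assumed** values, purely to show scale:

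| Net one-way share | m = 2 | m = 5 | m = 8 |
|---|---|---|---|
| 25% | 2 × 0.25 = 0.5 | 5 × 0.25 = 1.25 | 8 × 0.25 = 2.0 |
| 50% | 2 × 0.5 = 1.0 | 5 × 0.5 = 2.5 | 8 × 0.5 = 4.0 |
| 100% | 2 × 1 = 2.0 | 5 × 1 = 5.0 | 8 × 1 = 8.0 |

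Two yardsticks help in reading the table. Section 9.3.1 treats 5 points as a small but important change. With about 50 patients (9.5) and an assumed SD of change of 10 to 25, the 95% half-width of a mean change runs from 1.96 × 10/√50 = 2.8 to 1.96 × 25/√50 = 6.9 points. The table is exact for means. Section 9.7.5.1 plans medians, which would shift by m if everyone switched and otherwise by an amount that depends on the distribution.

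**Could the planned model repair it?** The mixed model in 9.7.5.2 is exploratory, is run only if feasible, and studies baseline characteristics. If all patients changed mode together after the first KCCQ, mode and visit would be the same contrast and no model term could separate them.

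**The case against.** The operational text mostly agrees with itself: 9.1, 9.4 and Table 2 all describe a structured interview by trained staff. One sentence in a description of the instrument says otherwise. If the interview text governs, the remaining contrast is phone against face to face, which may matter less than interview against self-completion. Whether a patient comes to the site also depends partly on where they receive care. That is fairly stable, so many patients may keep one mode throughout. The CRF is not shown and may record contact type. The study is descriptive, and 9.9 already discloses a further difficulty with baseline quality of life in patients already on treatment.

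Most of this stands, and it limits how far the point goes. A reader might infer that the first KCCQ is done in person at consent and the later ones by phone, so that mode changes systematically after baseline. The documents do not support that. They tie the first KCCQ to consent in timing only, and 9.2 allows virtual interviews. A reader might also take a bias of 0.5 to 8 points as an estimate. It is not one, because both inputs are assumed, and the upper end needs every patient to switch in the same direction at the largest assumed effect.

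The objection does not remove the contradiction, the unrestricted acceptance of both settings, or the absence of a mode variable from Table 2. Standard scripts and training make interviewers more alike. They do not make the modes equivalent.

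**Conclusion.** The point holds in a limited form. The protocol contradicts itself on how its primary instrument is administered, lets mode vary from visit to visit, and does not list mode among its variables. Because the primary result is uncontrolled within-patient change in KCCQ-OS, any net one-way shift in mode would be mixed with true change and, on the listed variables, could not be detected.

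The documents establish neither the size, the direction nor the frequency of a shift, so this is a possible bias of unknown size. It would be zero in the mean if patients keep their mode or if switches balance. The tabulated figures show only what would follow from the assumed inputs. The case for acting is that the remedy is cheap and that unrecorded mode cannot be recovered later.

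**What to change.** 1. Reconcile 9.3.1 with 9.1, 9.4 and Table 2 so that they say the same thing about how the KCCQ is administered. If more than one mode is allowed, name each.
2. Ask sites to use the same mode for a patient's first and later KCCQs where possible. Another mode should be accepted rather than losing the visit, since 9.7.4 allows no imputation.
3. Add a KCCQ mode field to Table 2 and the CRF, completed at every visit: self-completed, phone or virtual, face to face.
4. Repeat the descriptive change-from-baseline summary on pairs of visits in the same mode. Add a mode term to the exploratory mixed model only if mode varies within visits.

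The cost is revised wording, one CRF field, a little more analysis and slightly less flexibility for sites. The same-mode summary will rest on fewer than the expected 50 or so patients if some switch, so it should be reported beside the full summary and not in place of it.

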8. RESEARCH QUESTION AND OBJECTIVES

Hypothesis

There are not hypotheses to evaluate.

Research Question

What is the impact of tafamidis use in Colombian patients diagnosed with ATTR-CM on quality of life during two years of follow-up?

Primary objective

To describe the impact of tafamidis use in Colombian patients diagnosed with ATTR-CM on quality of life during two years of follow-up

Secondary objectives

- To describe the clinical and demographic characteristics of the patients at the moment of prescription of tafamidis
- To determine the treatment patterns to manage ATTR-CM before tafamidis prescription
- To evaluate the frequency of hospitalization and its causes during the follow-up period
- To describe the use of cardiovascular devices during follow-up of patients recruited in the study
- To outline the change in baseline for patients in cardiovascular functionality in patients prescribed tafamidis
- To measure the adherence of the patients to the therapy
- To describe the access barriers during the use of tafamidis

Exploratory objectives

- To analyze the relationship between baseline variables and patient and changes of quality of life and cardiovascular functionality

PFIZER CONFIDENTIAL

CT24-WI-GL02-RF01 6.0 Non-Interventional Study Protocol Template For Primary Data Collection Study 01-Aug-2023
Page 20 of 57

CLINICAL AND MEDICAL CONTROLLED DOCUMENT (CMCD) REQUIRED FORM/TEMPLATE

Identifier	Version	Title	Effective Date
CT24-WI-GL02-RF01	6.0	NON-INTERVENTIONAL STUDY PROTOCOL TEMPLATE FOR PRIMARY DATA COLLECTION STUDY	01-Aug-2023

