Cardiovascular devices during follow-up	Treatment	Medical record, Interview	Cardiac resynchronization therapy – defibrillator (CRT-D), Cardiac resynchronization therapy – pacemakers (CRT-P), implantable cardioverter defibrillator (ICD)
Date of prescription of tafamidis	Treatment	Interview	ddmm/yyyy

PFIZER CONFIDENTIAL

CT24-WI-GL02-RF01 6.0 Non-Interventional Study Protocol Template For Primary Data Collection Study 01-

Aug-2023

Page 27 of 57

**CLINICAL AND MEDICAL CONTROLLED DOCUMENT (CMCD)
REQUIRED FORM/TEMPLATE**

Identifier	Version	Title	Effective Date
CT24-WI-GL02-RF01	6.0	NON-INTERVENTIONAL STUDY PROTOCOL TEMPLATE FOR PRIMARY DATA COLLECTION STUDY	01-Aug-2023

Date of first administration of tafamidis	Treatment	Interview	ddmm/yyyy
Delay of supply of tafamidis	Treatment	Interview	Yes, No
Cause of delay	Treatment	Interview	Authorization, Treatment not available in the supplier, error of prescription, other
Adherence	Outcomes	Interview	%
Sum of QRS amplitude in I, II, and III leads at the end of follow-up	Clinical characteristic	Medical record, Interview	mm
Sum of QRS amplitude in all six limb leads at the end of follow-up	Clinical characteristic	Medical record, Interview	mm
Sum of QRS amplitude in all six precordial leads at the end of follow-up	Clinical characteristic	Medical record, Interview	mm
Sokolow-Lyon index low voltage criteria at the end of follow-up	Clinical characteristic	Medical record, Interview	mm
Persistence	Outcomes	Interview	Yes, No
Hospitalization	Outcomes	Interview	Yes, No
Cause of the hospitalization	Outcomes	Interview	Cardiovascular, Other
Date of hospitalization	Outcomes	Interview	Date of admission: dd-mm-yyyy Date of discharge: dd-mm-yyyy
Day(s) of hospitalization	Outcomes	Interview	Days
Quality of life (KCCQ-OS score per visit)	Outcomes	Interview	Score
6MWT [§]	Outcomes	Site	Meters
Scintigraphy (Perugini scale) [§]	Outcomes	Site	Grade 0 - 3

* Per visits, according to schedule of the study

§ According to medical criteria, considering that the physician may choose to perform a different test

PFIZER CONFIDENTIAL

CT24-WI-GL02-RF01 6.0 Non-Interventional Study Protocol Template For Primary Data Collection Study 01-

Aug-2023

Page 28 of 57

**CLINICAL AND MEDICAL CONTROLLED DOCUMENT (CMCD)
REQUIRED FORM/TEMPLATE**

Identifier	Version	Title	Effective Date
CT24-WI-GL02-RF01	6.0	NON-INTERVENTIONAL STUDY PROTOCOL TEMPLATE FOR PRIMARY DATA COLLECTION STUDY	01-Aug-2023

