11. MANAGEMENT AND REPORTING OF ADVERSE EVENTS/ADVERSE REACTIONS

REQUIREMENTS

The table below summarizes the requirements for recording safety events on the CRF and for reporting safety events on the non-interventional study (NIS) adverse event monitoring (AEM) Report Form to Pfizer Safety. These requirements are delineated for three types of events: (1) serious adverse events (SAEs); (2) non-serious AEs (as applicable); and (3) scenarios involving drug exposure, including exposure during pregnancy, exposure during breast feeding, medication error, overdose, misuse, extravasation, lack of efficacy, and occupational exposure. These events are defined in the section “Definitions of safety events.”

Safety event	Recorded on the CRF	Reported on the NIS AEM Report Form to Pfizer Safety within 24 hours of awareness
SAE	All	All
Non-serious AE	All	None
Scenarios involving exposure to a drug under study, including exposure during pregnancy, exposure during breast feeding, medication error, overdose, misuse, extravasation, lack of efficacy, and occupational exposure	All (regardless of whether associated with an AE), except occupational exposure	All (regardless of whether associated with an AE) Note: Any associated AE is reported together with the exposure scenario.

For each AE, the investigator must pursue and obtain information adequate both to determine the outcome of the AE and to assess whether it meets the criteria for classification as a SAE (refer to section "Serious Adverse Events" below).

Safety events listed in the table above must be reported to Pfizer within 24 hours of awareness of the event by the investigator **regardless of whether the event is determined by the investigator to be related to tafamidis**. In particular, if the SAE is fatal or life-threatening, notification to Pfizer must be made immediately, irrespective of the extent of available event information. This timeframe also applies to additional new (follow-up) information on

PFIZER CONFIDENTIAL

CT24-WI-GL02-RF01 6.0 Non-Interventional Study Protocol Template For Primary Data Collection Study 01-

Aug-2023

Page 39 of 57

**CLINICAL AND MEDICAL CONTROLLED DOCUMENT (CMCD)
REQUIRED FORM/TEMPLATE**

Identifier	Version	Title	Effective Date
CT24-WI-GL02-RF01	6.0	NON-INTERVENTIONAL STUDY PROTOCOL TEMPLATE FOR PRIMARY DATA COLLECTION STUDY	01-Aug-2023

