CT24-WI-GL02-RF01 6.0 Non-Interventional Study Protocol Template For Primary Data Collection Study 01-

Aug-2023

Page 41 of 57

**CLINICAL AND MEDICAL CONTROLLED DOCUMENT (CMCD)
REQUIRED FORM/TEMPLATE**

Identifier	Version	Title	Effective Date
CT24-WI-GL02-RF01	6.0	NON-INTERVENTIONAL STUDY PROTOCOL TEMPLATE FOR PRIMARY DATA COLLECTION STUDY	01-Aug-2023

- Medication error;
- Occupational exposure.

Abnormal test findings

The criteria for determining whether an abnormal objective test finding should be reported as an AE are as follows:

- Test result is associated with accompanying symptoms, and/or
- Test result requires additional diagnostic testing or medical/surgical intervention, and/or
- Test result leads to a change in study dosing or discontinuation from the study, significant additional concomitant drug treatment, or other therapy, and/or
- Test result is considered to be an AE by the investigator or sponsor.

Merely repeating an abnormal test, in the absence of any of the above conditions, does not constitute an AE. Any abnormal test result that is determined to be an error does not require reporting as an AE.

Serious adverse events

A SAE is any untoward medical occurrence in a patient administered a medicinal or nutritional product (including pediatric formulas) at any dose that:

- Results in death;
- Is life-threatening;
- Requires inpatient hospitalization or prolongation of hospitalization (see below for circumstances that do not constitute AEs);
- Results in persistent or significant disability/incapacity (substantial disruption of the ability to conduct normal life functions);
- Results in congenital anomaly/birth defect.

Medical and scientific judgment is exercised in determining whether an event is an important medical event. An important medical event may not be immediately life-threatening and/or result in death or hospitalization. However, if it is determined that the event may jeopardize the patient or may require intervention to prevent one of the other outcomes listed in the definition above, the important medical event should be reported as serious.

Examples of such events are intensive treatment in an emergency room or at home for allergic bronchospasm; blood dyscrasias or convulsions that do not result in hospitalization; or development of drug dependency or drug abuse.

PFIZER CONFIDENTIAL

CT24-WI-GL02-RF01 6.0 Non-Interventional Study Protocol Template For Primary Data Collection Study 01-

Aug-2023

Page 42 of 57

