**CLINICAL AND MEDICAL CONTROLLED DOCUMENT (CMCD)
REQUIRED FORM/TEMPLATE**

Identifier	Version	Title	Effective Date
CT24-WI-GL02-RF01	6.0	NON-INTERVENTIONAL STUDY PROTOCOL TEMPLATE FOR PRIMARY DATA COLLECTION STUDY	01-Aug-2023

Additionally, any suspected transmission via a Pfizer product of an infectious agent, pathogenic or non-pathogenic, is considered serious. The event may be suspected from clinical symptoms or laboratory findings indicating an infection in a patient exposed to a Pfizer product. The terms “suspected transmission” and “transmission” are considered synonymous. These cases are considered unexpected and handled as serious expedited cases by pharmacovigilance (PV) personnel. Such cases are also considered for reporting as product defects, if appropriate.

Hospitalization

Hospitalization is defined as any initial admission (even if less than 24 hours) to a hospital or equivalent healthcare facility or any prolongation to an existing admission. Admission also includes transfer within the hospital to an acute/intensive care unit (e.g., from the psychiatric wing to a medical floor, medical floor to a coronary care unit, neurological floor to a tuberculosis unit). An emergency room visit does not necessarily constitute a hospitalization; however, an event leading to an emergency room visit should be assessed for medical importance.

Hospitalization in the absence of a medical AE is not in itself an AE and is not reportable. For example, the following reports of hospitalization without a medical AE are not to be reported.

- Social admission (e.g., patient has no place to sleep)
- Administrative admission (e.g., for yearly exam)
- Optional admission not associated with a precipitating medical AE (e.g., for elective cosmetic surgery)
- Hospitalization for observation without a medical AE
- Admission for treatment of a pre-existing condition not associated with the development of a new AE or with a worsening of the pre-existing condition (e.g., for work-up of persistent pre-treatment lab abnormality)

Scenarios necessitating reporting to Pfizer Safety within 24 hours

Scenarios involving exposure during pregnancy, exposure during breastfeeding, medication error, overdose, misuse, extravasation, lack of efficacy, and occupational exposure are described below.

Exposure during pregnancy

An exposure during pregnancy (EDP) occurs if:

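### Table 2 reduces cause of hospitalisation to two codes and leaves the 9.3.1 definition unverifiable for elective status and for one-night stays

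*Protocol*

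**What the plan says.** One of the secondary objectives in Section 8 is "To evaluate the frequency of hospitalization and its causes during the follow-up period".

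Section 9.3.1 defines the outcome as "a nonelective admission to an acute care setting for medical therapy that results in at least a 24-hour stay". It then lists ten conditions, judged on the primary diagnosis, that make a hospitalisation cardiovascular. The last of the ten is a catch-all for other vascular reasons.

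Table 2 (Section 9.3) gives the fields: hospitalisation Yes/No; cause, coded "Cardiovascular, Other"; dates, as "Date of admission: dd-mm-yyyy Date of discharge: dd-mm-yyyy"; and number of days. The source for all four is the interview. Section 9.4 adds that what the patient reports is confirmed against a summary of the medical records.

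Section 11 uses the same word for safety purposes: "any initial admission (even if less than 24 hours) to a hospital or equivalent healthcare facility or any prolongation to an existing admission". This feeds the seriousness criterion "Requires inpatient hospitalization or prolongation of hospitalization".

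**The concern.** The outcome definition in 9.3.1 sets conditions that the listed fields do not capture. No field holds elective or nonelective status, and the dates carry no clock time. The objective asks for causes, but the cause field has two values.

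The protocol also gives one word two meanings. It does not say which one governs the Yes/No item in Table 2. One site might enter only stays that meet 9.3.1, and another might enter every admission. The hospitalisation count would then partly reflect site habit. The same applies to the 12 months before the index date, for which Section 9.1 also collects hospitalisation frequency.

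At stake are a named secondary outcome and whether the report can separate, for example, heart failure admissions from stroke admissions. A statistical analysis plan cannot repair this afterwards, because it cannot derive what was not collected.

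**Working it through.** The plan gives no figure to reproduce here. The study is descriptive, with no sample size calculation and no assumed event rate. The check compares the definitions with the fields.

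**1. Each 9.3.1 condition against Table 2**

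| Condition in 9.3.1 | Field in Table 2 | Can it be verified? |
|---|---|---|
| Nonelective | None | No, for any stay |
| At least 24 hours | Dates without times; days | Depends on the dates (step 2) |
| Cardiovascular by primary diagnosis | Two-value cause code | The code can be assigned; the diagnosis behind it is not kept |

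**2. What dates say about a 24-hour stay**

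Let *a* be the clock time of admission and *d* that of discharge, both between 0 and 24 hours, and let *k* be the difference between the two dates. Then stay = 24*k* + *d* − *a*.

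- *k* = 0: stay = *d* − *a*, always under 24 hours.
- *k* = 1: stay = 24 + *d* − *a*, from just over 0 to just under 48 hours.
- *k* = 2 or more: stay always over 24 hours.

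Only one-night stays (*k* = 1) are undetermined. Admission at 23:00 and discharge at 06:00 gives 24 + 6 − 23 = 7 hours. Admission at 08:00 and discharge at 20:00 the next day gives 24 + 20 − 8 = 36 hours. Both have the same date difference, and a count of days derived from the dates does not separate them.

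**3. How often a one-night stay would meet the rule**

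The documents give no clock times, so this step rests on assumptions. If *a* is uniform over the day and independent of *d*, a one-night stay lasts at least 24 hours when *d* is at or after *a*, with probability E(*d*)/24.

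- Discharge uniform over 0 to 24 h: 12/24 = 50%.
- Discharge uniform over 8 to 18 h: 13/24 = 54%.
- Discharge uniform over 10 to 16 h: 13/24 = 54%.

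A simulation under the same assumptions gave 0.500, 0.542 and 0.542. For a one-night stay, the dates are therefore close to uninformative about the 24-hour rule.

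**4. Cause detail**

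The list has ten entries: heart failure; arrhythmia; transient ischaemic attack; stroke; myocardial infarction; unstable angina; pulmonary embolism or peripheral arterial/vascular disease; peripheral emboli; venous thrombosis; other vascular. All ten map to one code, and everything else maps to the second. The ENCePP checklist in Annex 2 answers No to a coding system for outcomes, so it points to no other route to the detail.

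**5. Weight of one misclassified patient**

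Section 9.5 expects close to 50 patients. 1/50 = 2 percentage points in the proportion hospitalised, provided the doubtful stay is the only one that decides that patient's status.

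**The case against.** The strongest reply is that the two definitions serve different purposes. Section 9.3.1 describes a study outcome; Section 11 decides when an adverse event is serious. Having both is normal, and neither claims to govern the other. This stands. What is missing is a link between them and a statement of which one applies to the Table 2 item.

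A reader might go further and infer that serious adverse events with short stays would be lost. The protocol does not support that. Section 11 expressly includes stays under 24 hours, requires all serious events on the CRF, and states that "Safety events listed in the table above must be reported to Pfizer within 24 hours of awareness of the event by the investigator". Nothing makes detection of these events depend on the Table 2 item. The remaining risk is confusion at sites and counts that do not match between outcome and safety data.

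A second reply is that sites can apply 9.3.1 when they enter the data. Staff are trained, two centres validate the CRF, and reports are confirmed against a record summary. This also stands in part, so it would be wrong to say that the rule cannot be applied. But a judgement made at entry leaves no field against which it can be checked later. Section 9.9 also concedes that completeness depends on the records patients provide.

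A third reply is that the ten conditions are a decision rule for the cardiovascular code and not a coding frame. This is a fair reading, and the list can be used that way. Some sub-cause detail may also sit in the serious adverse event reports, but the protocol does not plan to use those for this objective.

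Finally, Table 2 is a variable list and the CRF itself is not shown. It may contain more fields.

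**Conclusion.** The point holds in a limited form. If the protocol is followed exactly as Table 2 stands:

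- causes of hospitalisation can be reported only as cardiovascular versus other;
- the nonelective condition cannot be verified for any stay;
- the 24-hour condition cannot be verified for one-night stays, but is settled by dates for all others.

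It would be too strong to say that the causes objective cannot be answered. It can be, at two levels. The two uses of the word are not a contradiction either; they are unlinked, which invites inconsistent entry across about six sites.

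The numerical effect on the outcome cannot be estimated, because the documents give no frequency of one-night or elective admissions. The 2 percentage points per patient and the 50% to 54% are illustrations under the stated assumptions. The conclusion also assumes that the CRF follows Table 2. The change is worth making because it is cheap and widens what the study can report.

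**What to change.** Keep one log of every admission, whatever its length, with these items:

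- elective, yes/no;
- stay of 24 hours or more, yes/no, or admission and discharge times;
- primary diagnosis, coded to the 9.3.1 categories plus non-cardiovascular (specify).

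Derive the 9.3.1 outcome from this log in the analysis, so that sites do not filter at entry. Add to 9.3.1 that its definition applies to the descriptive outcome only and that recording and reporting of serious adverse events follow Section 11. Amend Table 2 to match.

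The cost is three or four extra CRF fields and a sentence each in 9.3.1 and Table 2. No new procedure is needed, since Section 9.4 already has hospitalisations confirmed against the record summary. With about 50 patients, some cause categories will hold few or no events. They can be shown as counts or grouped in the report, which a two-value field does not allow.
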